## **Criteria for Evaluation:**

Details of time points for trial activities and assessments are provided in Section 2.1 (Core Phase) and Section 2.2 (Extension Phase).

Efficacy will be assessed by FVC, 6MWT, PFS, patient-reported outcomes (K-BILD, L-IPF, LCQ, and SF-12), respiratory-related hospitalization, TOR, DLCO, IPF-related acute exacerbation, all-cause mortality, mortality due to respiratory deterioration, mortality due to IPF-related events and lung HRCT.

Blood samples for fipaxalparant (HZN-825) PK assessment, pharmacodynamic markers, and optional pharmacogenetic assessment (for drug metabolizing enzymes and/or transporters) will be collected.

Safety will be assessed via AEs, concomitant medication use, physical examinations, vital signs, orthostatic hypotension assessment, laboratory evaluations, 12-lead ECG, and echocardiogram.

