# 8.1.2 Secondary Objectives

- 1. Evaluate the effect of 2 dose regimens of fipaxalparant (HZN-825) versus placebo on the proportion of subjects with decline in FVC % predicted ≥10% from Baseline after 52 weeks of treatment.
- 2. Evaluate the effect of 2 dose regimens of fipaxalparant (HZN-825) versus placebo on the changes from Baseline in the 6-Minute Walk Test (6MWT) after 52 weeks of treatment.
- 3. Evaluate the effect of 2 dose regimens of fipaxalparant (HZN-825) versus placebo on the King's Brief Interstitial Lung Disease Questionnaire (K-BILD) after 52 weeks of treatment.
- 4. Evaluate the effect of 2 dose regimens of fipaxalparant (HZN-825) versus placebo on the living with IPF (L-IPF) after 52 weeks of treatment.
- 5. Evaluate the effect of 2 dose regimens fipaxalparant (HZN-825) versus placebo on the Leicester Cough Questionnaire (LCQ) after 52 weeks of treatment.
- 6. Evaluate the effect of 2 dose regimens of fipaxalparant (HZN-825) versus placebo on the rate of hospitalization due to respiratory distress up to 52 weeks of treatment.
- 7. Evaluate the effect of 2 dose regimens of fipaxalparant (HZN-825) versus placebo on the composite endpoint of progression-free survival (PFS), where progression includes decline in FVC % predicted ≥10% from Baseline or death over 52 weeks of treatment.
- 8. Assess safety and tolerability of fipaxalparant (HZN-825), inclusive of, but not limited to, AEs, SAEs, and AESI.
- 9. Evaluate the PK of fipaxalparant (HZN-825).

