# 9.6.1.4 Secondary Efficacy Endpoint Analyses

The key secondary endpoint will be the proportion of subjects with decline in FVC % predicted ≥10% from Baseline at Week 52 and will be analyzed using a logistic regression model with treatment group and stratified by factors used for stratifying the randomization. The logistic model will provide odds ratio, its 90% CI and p-value for comparing each fipaxalparant (HZN-825) group with the placebo group. Statistical significance for the key secondary endpoint will only be concluded if statistical significance is achieved for the primary efficacy endpoint.

Changes from Baseline in 6MWT, K-BILD, L-IPF, and LCQ scores will be analyzed analogously to the primary efficacy endpoints. Survival analysis will be used for the time-to-event endpoints, including time to the first onset of the composite endpoint and the time to the first hospitalization due to respiratory distress. A Cox proportional hazard model stratified like the previous logistic model with treatment group will provide hazard ratio, its 90% CI and p-value to compare each fipaxalparant (HZN-825) group with the placebo group.

Date: 07 October 2024 IND 154671

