2.5. Changes from the Protocol Planned Analyses

The definition of HZN-825 Baseline has been updated from the protocol. This adjustment is essential to facilitate a comprehensive comparison of data over 104 weeks across all cohorts. As a result, HZN-825 Baseline has been redefined as the latest measurement prior to the first dose of study drug (either HZN-825 or Placebo) during the Core Phase.

For efficacy analysis, the prior use of IPF approved therapy will be used as a covariate in the mixed model for repeated measures instead of concomitant use of IPF approved therapy. In earlier protocol versions, the prior use of IPF approved therapy was used as a stratification factor, while concomitant use of IPF approved therapy was restricted. In protocol version 4, concomitant use of IPF approved therapy was permitted and used as a stratification factor. However, only a small number of enrolled subjects were on concomitant IPF therapy. To ensure a robust model estimate, the prior use of IPF approved therapy will be used in the model. Additional subgroup analysis will be conducted as needed, focusing on subjects who were on concomitant use of IPF approved therapy.

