3.4. Multiplicity Adjustment

The overall statistical level is α =0.10 (2-sided). Because 2 dose regimens of HZN-825 will be compared to placebo, a hierarchical testing procedure will be used for multiple comparisons. Therefore, α =0.10 (2-sided) will be used in the analysis. The hierarchical testing procedure will be used for the primary and key secondary endpoint. For the primary endpoint, the BID dose will be tested versus placebo first; if significant, the QD dose will then be tested. If 1 or 2 dose regimens of the primary endpoint are not rejected after completing testing, no further testing will occur. If both HZN-825 doses are statistically significantly better than placebo for primary efficacy endpoint, the testing procedure will continue for the key secondary endpoint and will be similar to that performed for the primary endpoint.

Although p-values will be provided for the other secondary and exploratory endpoints, they will not be used for inferential purposes.

Version 2.0

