6.1.2. Secondary Efficacy Endpoints

6.1.2.1. Key Secondary Endpoint: Proportion of Subjects with Decline in FVC% Predicted ≥10% from Baseline at Week 52

The proportion of subjects with a decrease in FVC% predicted \geq 10% from baseline at Week 52 will be analyzed with observed data using a stratified logistic regression model. Baseline value and treatment will be considered as factors in the model and prior use of approved IPF therapy [yes or no], FVC% predicted at baseline [\geq 70, <70] will be considered as stratification factors.

Version 2.0

The odds ratio between each dose and placebo with its 90% confidence intervals and P-value will be presented. Subjects missing FVC% predicted values at Week 52 will be imputed as non-responders.

The proportion of subjects with a decrease in FVC% predicted ≥10% from baseline predicted will also be summarized descriptively for observed cases at each visit.

6.1.2.2. Change From Baseline in the 6 Minute Walk Test (6MWT) Results to Week 52

The 6MWT measures the distance a subject can quickly walk on a flat, hard surface in 6 minutes (6-minute walk distance). This test evaluates the global and integrated responses of all the systems involved during exercise, including the pulmonary and cardiovascular systems, systemic circulation, peripheral circulation, blood, neuromuscular units and muscle metabolism. The 6MWT will be performed according to American Thoracic Society (ATS) guidelines for the 6MWT (LH, 2018)

The distance walked by the 6MWT will be tested in the same manner as that described for the primary analysis of the primary endpoint in Section 6.1.1.1, but based only on observed data and including the covariate of oxygen flow rate in the model. For subjects who aren't on supplemental oxygen (SpO2) at the visit, 0 liters per minute will be imputed for their oxygen flow rate. Descriptive statistics for the observed results and change from Baseline in the absolute distance walked of the 6MWT will be summarized for each visit.

Values corresponding to the 6MWT including baseline (prior to test) dyspnea, baseline (prior to test) fatigue, baseline (prior to test) SpO2, baseline (prior to test) heart rate, end of test dyspnea, end of test fatigue, end of test heart rate, and end of test SpO2 will be summarized at each visit for the observed results and change from Baseline.

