6.1.2.3. Change from Baseline in King's Brief Interstitial Lung Disease (K-BILD)
Questionnaire Total Score to Week 52

The K-BILD is a self-completed health status questionnaire comprising 15 items, each with a 7-point Likert response scale that was developed and validated specifically for patients with IPF (Patel AS, 2012). The response options vary, but in general 1 = worst disease impact and 7 = least disease impact. This questionnaire has 3 domains: psychological, breathlessness and activities and chest symptoms. The K-BILD domains and total score range from 0 to 100; 100 represents best health status.

The K-BILD scoring has recently changed with the introduction of a logit transformation step. The minimal clinically important difference for the K-BILD total score (logit version), as determined by both anchor and distribution-based methods, is a change of 5 units [Sinha et al., 2019].

The K-BILD total score will be tested in the same manner as that described for the primary analysis of the primary endpoint in Section 6.1.1.1, but based only on observed data.

Version 2.0

Descriptive statistics for the observed results and change from Baseline in the K-BILD total score and each domain score will be summarized for each visit.

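### As naturally read, the 6MWT model adjusts for oxygen flow measured after randomisation, so if treatment changes oxygen use it may not estimate the total effect on walk distance

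*SAP*

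**What the plan says.** The objective in protocol 8.1.2 is to "Evaluate the effect of 2 dose regimens of fipaxalparant (HZN-825) versus placebo on the changes from Baseline in the 6-Minute Walk Test (6MWT") at 52 weeks. For the analysis, protocol 9.6.1.4 says: "Changes from Baseline in 6MWT, K-BILD, L-IPF, and LCQ scores will be analyzed analogously to the primary efficacy endpoints". The primary model in protocol 9.6.1.3 has no oxygen term.

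SAP 6.1.2.2 takes the primary model for walk distance, but "based only on observed data and including the covariate of oxygen flow rate in the model". It adds that, for subjects who are not "on supplemental oxygen (SpO2) at the visit, 0 liters per minute will be imputed for their oxygen flow rate". Neither sentence mentions baseline.

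Related text:

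- SAP 6.1.1.1 labels the FVC covariate of the same model as a baseline value.
- SAP 6.1.1.2 makes treatment policy the general strategy for efficacy endpoints.
- SAP 2.5, on changes from the protocol, declares one covariate change: "For efficacy analysis, the prior use of IPF approved therapy will be used as a covariate in the mixed model for repeated measures". It does not list oxygen flow.
- The questionnaire endpoints get no extra covariate, for example: "The K-BILD total score will be tested in the same manner as that described for the primary analysis of the primary endpoint".
- The protocol synopsis counts titrated oxygen requirement (TOR) among the efficacy measures: "Efficacy will be assessed by FVC, 6MWT, PFS, patient-reported outcomes (K-BILD, L-IPF, LCQ, and SF-12), respiratory-related hospitalization, TOR, DLCO".
- SAP 3.4 sets the status of 6MWT: "Although p-values will be provided for the other secondary and exploratory endpoints, they will not be used for inferential purposes".

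**The concern.** A covariate measured after randomisation can itself be changed by treatment. If the drug slows progression, treated subjects may need less oxygen. A model that holds visit-level flow equal across arms then removes, or distorts, part of the effect it is meant to estimate. The result answers a different question: the difference between arms among subjects using the same oxygen flow. That is neither the stated objective nor the treatment policy strategy.

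The covariate is also not identifiable from the text. TOR is titrated with the subject standing (protocol 9.5.1.3), which is not the flow used during a walk. The SAP abbreviation list expands SpO2 as supplemental oxygen, while the protocol uses that symbol for oxygen saturation.

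At stake is the only model-based 6MWT estimate that SAP 6.1.2.2 specifies, with its confidence interval. The descriptive summaries by visit are the only unadjusted results in that section.

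**Working it through.** **Plan's own figures.** None is given for 6MWT. SAP 1.3 covers FVC only. Its figures reproduce: SE = 9 × √(2/45) = 1.897, so Φ(2/1.897) = 85.4%, Φ(1/1.897) = 70.1% and 1 − Φ(2/1.897) = 14.6%, against 85%, 70% and 15% stated. Nothing below depends on them.

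**Timing.** The zero-flow rule is tied to the visit, and the FVC term in the same model is marked as baseline while the oxygen term is not. An analyst following the text would use each visit's flow.

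**Formula.** In the linear model at Week 52:

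adjusted effect = total effect − (flow coefficient × treatment effect on flow)

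The two effects agree only if treatment does not change flow or if flow is unrelated to distance given treatment.

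**First calculation.** Large-sample simulation of 60,000 subjects, with repeated-measures GLS and unstructured covariance at the post-baseline 6MWT visits (Weeks 16, 28 and 52). All inputs are assumed. Week 52 results:

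| Scenario | Total (m) | Flow difference (L/min) | Flow coefficient (m per L/min) | Adjusted for visit flow (m) |
|---|---|---|---|---|
| A. Treatment does not change flow | 24.8 | 0.00 | −9.8 | 24.8 |
| B. Flow lowered; flow marks severity | 25.1 | −0.35 | −9.5 | 21.8 |
| C. As B, larger change | 25.4 | −0.65 | −9.0 | 19.5 |
| D. Flow lowered; oxygen lengthens the walk; no shared severity | 21.6 | −0.36 | 5.1 | 23.4 |
| E. No true effect on distance; flow lowered; flow marks severity | −0.3 | −0.36 | −9.3 | −3.6 |
| F. Flow raised; flow marks severity | 25.1 | 0.42 | −9.7 | 29.2 |

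The formula reproduces these. For B, 25.1 − (−9.5 × −0.35) = 25.1 − 3.3 = 21.8. For D, 21.6 − (5.1 × −0.36) = 21.6 + 1.8 = 23.4. With baseline flow, or no flow term, the estimate was within 0.1 m of the total in all six scenarios.

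**Second calculation.** A wider grid with the same visits and model type. Assumptions:

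- Treatment slows latent progression by 0.5 at Week 52 (placebo SD 0.89), and 30 m are lost per unit of progression.
- Flow is truncated at zero and rises 0.5, 1 or 2 L/min per unit of progression.
- 10%, 20%, 35% or 50% of placebo subjects are on oxygen at Week 52.
- Oxygen adds 0, 5, 10 or 20 m per L/min.

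That makes 3 × 4 × 4 = 48 scenarios, run under two models, so 96 in all, with total effects of 6 to 16 m:

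| Model for flow | Ratio of adjusted to total | Shrunk / unchanged / inflated |
|---|---|---|
| Baseline severity plus progression (400,000 subjects per scenario) | 0.73–1.44 | 40 / 1 / 7 |
| Progression only (120,000 per scenario) | 0.48–1.02 | 47 / 0 / 1 |
| Both | 0.48–1.44 | 87 / 1 / 8 |

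- With 10% to 20% of placebo subjects on oxygen the ratio was 0.77–1.08; with 35% to 50% it was 0.48–1.44.
- All 8 inflated scenarios assumed 20 m per L/min. With 0 to 10 m per L/min the ratio was 0.48–0.97.
- With baseline flow the ratio was 1.00 in all 48 scenarios checked (first model).
- With no treatment effect at all (3 scenarios per model), adjusted and unadjusted estimates were within 0.25 m of zero. Scenario E shows that this does not extend to a drug that changes flow but not distance.

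**The case against.** **The visit-level reading is an inference.** A zero-flow rule would also be needed on Day 1, and if Day 1 flow was meant the bias disappears. That is true, but the text points to visit values and would be programmed that way, so it needs changing under either reading.

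**An oxygen term suits an exercise test.** Walk distance can depend on the oxygen delivered, which may explain why the questionnaires have no such term. The contrast with them is therefore weak support. Comparing arms at equal oxygen flow is a fair supplementary question; it should not be the only modelled answer to the objective. One may also argue that an analogous analysis in the protocol need not have an identical covariate list. Even so, SAP 2.5 records a comparable change and omits this one.

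**A model without flow may exist elsewhere.** Parts of the exploratory sections are redacted and the TLF shells are not available, so the statement is limited to SAP 6.1.2.2.

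**The size is assumed and small beside sampling error.** This stands. The assumed effect on progression is 0.5/0.89 = 0.56 SD, against 3/9 = 0.33 SD for the design difference in FVC. If the SD of 6MWT change is taken as 60 to 100 m, the SE with 45 per arm is SD × √(2/45) = 12.6 to 21.1 m. At 10% to 20% oxygen use the shift is at most 0.23 × 16 = 3.7 m, below 0.3 SE. The largest shrinkage is at most 0.52 × 16 = 8.3 m, below one SE. The discrepancy is nonetheless systematic and avoidable.

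**The consequence is limited.** This also stands: the p-value is not inferential, and readers will see unadjusted summaries by visit.

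**Conclusion.** The concern holds. As naturally read, the specified 6MWT model conditions on a post-randomisation variable that treatment may change, and it then need not estimate the regimen effect named in the objective. This requires three things: visit-level flow is used, treatment changes flow, and flow is related to distance given treatment.

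The direction is not fixed. Shrinkage toward no effect is the more likely result; inflation is possible if oxygen strongly improves distance or if treatment raises flow. The ranges reported here illustrate assumptions and are not estimates for this trial, because the documents give no oxygen prevalence, 6MWT variability or oxygen benefit. The primary and key secondary analyses and the type I error rate are unaffected. The SAP should be corrected, but the main conclusions do not depend on it. Confidence is medium, because the timing of the covariate is inferred.

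**What to change.** In SAP 6.1.2.2:

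1. State the time point and source of the flow value, naming either the flow used in the walk or the titrated requirement.
2. In the main 6MWT model, replace visit-level flow with Day 1 flow from that source (0 L/min if none). If Day 1 flow was not recorded, drop the term.
3. Keep visit-level flow only in a supplementary analysis, labelled as a comparison at equal oxygen flow.
4. Show oxygen use by arm and visit descriptively, if this is not already planned.

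In SAP 2.5, record the difference from protocol 9.6.1.4.

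Separately, and for precision only, add Day 1 walk distance as a covariate.

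The correction to the main model costs one SAP sentence and one line in SAP 2.5; the supplementary model and any new oxygen table add a little programming. No new data are needed. The 6MWT and TOR are both scheduled on Day 1 (protocol 2.1). The documents do not say whether flow during the Day 1 walk is recorded, hence the option to drop the term.

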6.1.2.3. Change from Baseline in King's Brief Interstitial Lung Disease (K-BILD)
Questionnaire Total Score to Week 52

The K-BILD is a self-completed health status questionnaire comprising 15 items, each with a 7-point Likert response scale that was developed and validated specifically for patients with IPF (Patel AS, 2012). The response options vary, but in general 1 = worst disease impact and 7 = least disease impact. This questionnaire has 3 domains: psychological, breathlessness and activities and chest symptoms. The K-BILD domains and total score range from 0 to 100; 100 represents best health status.

The K-BILD scoring has recently changed with the introduction of a logit transformation step. The minimal clinically important difference for the K-BILD total score (logit version), as determined by both anchor and distribution-based methods, is a change of 5 units [Sinha et al., 2019].

The K-BILD total score will be tested in the same manner as that described for the primary analysis of the primary endpoint in Section 6.1.1.1, but based only on observed data.

Version 2.0

Descriptive statistics for the observed results and change from Baseline in the K-BILD total score and each domain score will be summarized for each visit.

6.1.2.4. Change from Baseline in the Living with Pulmonary Fibrosis (L-IPF)
Questionnaire Symptoms Total and Impacts Total Score to Week 52

The L-IPF is a validated questionnaire that assesses symptoms, disease impacts and health-related quality of life in subjects with IPF (Swigris JJ, 2020). This questionnaire was developed with input from the FDA and comprises 2 modules: a 15-item symptom module with 3 domains (dyspnea, cough and energy), all with a 24-hour recall, and a 20-item impacts module with 1-week recall. All items in both modules have response options in a 5-point (0-4) numerical rating scale format. The L-IPF yields five scales (symptoms total, dyspnea, cough, energy, and impacts total); raw scores for each are transformed to a model-based scale ranging from 0 to 100 with a mean of 50 and an SD of 10. For each scale, tables are used to convert raw scores, and higher scores indicate greater impairment.

The absolute change from Baseline in the L-IPF impacts total score, the L-IPF symptoms total score at week 52 will be computed and evaluated in the same manner as that described for the primary analysis of the primary endpoint in Section 6.1.1.1 but based only on observed data. Descriptive statistics for the observed results and change from baseline in the the L-IPF impact score, the L-IPF symptoms total score and the L-IPF symptoms domain scores will be summarized for each visit.

6.1.2.5. Change from Baseline in Leicester Cough Questionnaire (LCQ) Total Score to Week 52

The LCQ is a patient-reported questionnaire evaluating the impact of cough on quality of life. This questionnaire was originally developed for use in people with idiopathic chronic cough and has since been validated for use in people with bronchiectasis and chronic obstructive pulmonary disease (Birring SS, 2003).

The LCQ comprises 19 items and takes 5 to 10 minutes to complete. Each item assesses symptoms or the impact of symptoms over the last 2 weeks on a 7-point Likert scale. Scores in 3 domains (physical, psychological and social) are calculated as a mean for each domain (range: 1 to 7). A total score (range: 3 to 21) is also calculated by summing the domain scores. Higher scores indicate better quality of life.

The LCQ total score will be tested in the same manner as that described for the primary analysis of the primary endpoint in Section 6.1.1.1, but based only on observed data. Descriptive statistics for the observed results and change from Baseline in the LCQ total score and each domain score will be summarized for each visit.

6.1.2.6. Time to First Hospitalization Due to Respiratory Distress from Baseline up to Week 52

Hospitalization due to respiratory distress is defined as a non-elective hospitalization lasting more than 24 hours in a hospital, emergency room or observation unit, due to respiratory

Version 2.0

causes that occur after randomization. Adverse events identified as leading to hospitalization due to respiratory distress will be adjudicated to confirm that the event and hospitalization meet the stated criteria.

A Cox proportional hazard model stratified by prior use of approved IPF therapy [yes or no] and FVC% predicted at baseline [\geq 70, <70] and treatment group as factors will provide the hazard ratio, its 90% CI and p-value to compare each HZN-825 group with the placebo group.

A subject will be considered as meeting the event criteria if the adjudication committee identifies any adverse event as leading to hospitalization due to respiratory distress. The start date of the hospitalization will be day of the event. In all other cases, the subject will be considered censored, and their last date of contact in the study (either date of safety follow-up if the subject doesn't enter the extension study or the Week 52 visit date for subjects that enter the extension) will be the date of censoring.

A corresponding Kaplan-Meier plot will be created to supplement the analysis, along with a summary of the quartiles of the Kaplan-Meier time to event estimate.

6.1.2.7. Composite Endpoint: Progression Free Survival (PFS) from Baseline up to Week 52, where Progression Includes Decline in FVC % Predicted ≥ 10% or Death

A Cox proportional hazard model stratified by concomitant use of approved IPF therapy [yes or no] and FVC% predicted at baseline [\geq 70, <70] and treatment group as factors will provide the hazard ratio, its 90% CI and p-value to compare each HZN-825 group with the placebo group.

[figure not shown]
The time-to-progression will be defined as the duration from the date of first dose of study drug to either (a) the date of the visit where FVC % predicted declines $\geq 10\%$ from Baseline or (b) the date of subject death, whichever occurs earlier. Subjects who do not experience either of these events will be considered censored at the time and their last date of contact in the study (either date of safety follow-up if the subject doesn't enter the extension study or the Week 52 visit date for subjects that enter the extension) will be the date of censoring.

A corresponding Kaplan Meier plot will be created to supplement the analysis.

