# 9.5.5.1.1.2 Serious Adverse Event Definition

A TEAE, baseline event or suspected adverse reaction is considered serious if, in the view of either the Investigator or Sponsor, it results in any of the following:

- Death. This includes any death that occurs during the conduct of a clinical trial, including deaths that appear to be completely unrelated to the trial drug (e.g., car accidents).
- Life-threatening adverse experience. An AE or suspected adverse reaction is considered life-threatening if, in the view of either the Investigator or the Sponsor, its occurrence places the subject at immediate risk of death. It does not include an AE or suspected adverse reaction that, had it occurred in a more severe form, might have caused death.
- Persistent or significant disability or incapacity.
- Inpatient hospitalization or prolongation of an existing hospitalization.
- Congenital anomaly or birth defect.
- Other medically important event that, according to appropriate medical judgment, may require medical or surgical intervention to prevent one of the outcomes listed above.

Surgical procedures or other therapeutic interventions themselves are not AEs, but the condition for which the surgery/intervention is required is an AE and should be documented accordingly.

Elective surgeries that require hospitalization and treatment received at an emergency room or similar facility will not be considered as SAEs unless one of the definitions of an SAE listed above is met.

In addition, hospitalizations for planned procedures are not considered an AE, unless they are prolonged hospitalizations and emergency room visits <24 hours in duration are not considered hospitalizations.

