# 17.2 Hospitalization Due to Respiratory Distress

Hospitalization due to respiratory distress is defined as a non-elective hospitalization lasting more than 24 hours in a hospital, emergency room or observation unit, due to respiratory causes that occur after randomization.

Clinical information for potential hospitalization due to respiratory distress will be collected on a dedicated questionnaire. In addition, all relevant clinical data (summary on clinical course, signs and symptoms; laboratory, lung function and imaging results; and treatment provided) relating to the hospitalization will be collected and provided to an independent adjudication committee for review.

[figure not shown]
Clinical information related to potential respiratory related hospitalizations will be provided to an independent adjudication committee for review in accordance with the standardized algorithm proposed by Kreuter et al., 2020 (Figure 17.1). For additional details, refer to the adjudication committee charter.

Fipaxalparant (HZN-825)

Version 5.0, Amendment 4

Protocol: HZNP-HZN-825-303

Figure 17.1 Algorithm for Adjudication of Respiratory-related Hospitalization in Idiopathic Pulmonary Fibrosis

\*Presenting to ER elective or non-elective. Elective (non-emergency) admission to hospital for lung transplantation is excluded.

Note that for the sake of simplicity, 'extra-parenchymal' and 'other respiratory' are both considered respiratory causes of hospitalization, together with AEIPF ('definite' or 'suspected', in which both are either 'triggered' or 'idiopathic'). All other admissions are 'non-respiratory' and classed as such. AE, acute exacerbation; CCF, congestive cardiac failure; DAD, diffuse alveolar damage; ER, emergency room; IPF, idiopathic pulmonary fibrosis; LV, left ventricular; MI, myocardial infarction; PE, pulmonary embolism.

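### A first respiratory admission that ends in death within 24 hours is, as the text stands, censored in the time-to-respiratory-hospitalisation analysis, and the listed censoring dates do not fit a subject who died

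*SAP*

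**What the plan says.** SAP 6.1.2.6 and Protocol 17.2 share one definition of the event. The SAP puts it this way: "Hospitalization due to respiratory distress is defined as a non-elective hospitalization lasting more than 24 hours in a hospital, emergency room or observation unit". The cause must be respiratory and the onset after randomisation. Neither section mentions a stay that is short because the subject died.

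The SAP then sets three rules:

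- **Adjudication.** Adverse events put forward as leading to such a hospitalisation "will be adjudicated to confirm that the event and hospitalization meet the stated criteria".
- **Event.** The test is the committee's finding: "A subject will be considered as meeting the event criteria if the adjudication committee identifies any adverse event as leading to hospitalization due to respiratory" (quote cut one word short). The event is dated at the start of the hospitalisation.
- **Censoring.** "In all other cases, the subject will be considered censored" at the last date of contact, which is spelled out as "either date of safety follow-up if the subject doesn't enter the extension study or the Week 52 visit date for subjects that enter the extension".

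Protocol 17.2 adds that the committee follows a published standardised algorithm (Figure 17.1) and refers to the adjudication charter for details. Neither the figure nor the charter can be seen.

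**The concern.** The 24-hour threshold is presumably there to keep out short observation stays. Applied as written, it also excludes an admission that was short only because it was fatal. Two subjects with the same acute exacerbation would then be classified in opposite ways: the one discharged on day 3 has an event, and the one who dies on the first day does not.

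That second subject leaves the risk set as though censoring were unrelated to respiratory hospitalisation, when in fact such an admission has just occurred. With few events per arm, a single case of this kind can shift the hazard ratio noticeably. The arm with more rapidly fatal admissions would look better on this endpoint.

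**Working it through.** The plan states no event rate, hazard ratio or power for this endpoint, so there is no figure to reproduce. The check is mainly one of reading the rules together.

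**Step 1: apply the rules to four records.**

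| Record | More than 24 hours? | Result under SAP 6.1.2.6 |
|---|---|---|
| A. First respiratory admission, discharged on day 3 | Yes | Event at admission |
| B. First respiratory admission, death at hour 18 | No | Censored; date not defined |
| C. Earlier qualifying admission, then a fatal short one | Yes, for the first | Event at the first admission |
| D. Respiratory death with no admission | No admission | Censored; date not defined |

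Record B is the gap. Record C shows its limit: it arises only when the subject has no earlier qualifying admission.

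**Step 2: is the strict reading fair?** Duration is one of the stated criteria that adjudication must confirm. The protocol also takes 24 hours seriously elsewhere: its serious adverse event definition (9.5.5.1.1.2) says that "emergency room visits <24 hours in duration are not considered hospitalizations", and the form in 17.10 describes hospitalisation as an admission of longer than 24 hours. The strict reading is not strained.

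**Step 3: the censoring date.** The only dates offered are the safety follow-up visit and, for those entering the extension, the Week 52 visit. A subject who died will usually have neither, so for records B and D the programmer would have to choose a date. SAP 6.1.3.6 (time to respiratory death) borrows this approach, so deaths from other causes meet the same problem there.

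**Step 4: size, on assumed counts.** There are 45 subjects per arm (SAP 1.3). Assume that 10% to 15% have a first respiratory admission: 45 × 0.10 = 4.5 and 45 × 0.15 = 6.75, about 5 to 7 per arm. One lost event is then 1/7 = 14% to 1/5 = 20% of that arm's count.

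For the hazard ratio, let both arms truly have n such admissions (true ratio 1.00) and let one in a single arm be censored. Approximate ratio, affected arm over the other = ln(1 − (n − 1)/45) / ln(1 − n/45):

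| n per arm | Early death on active | Early death on placebo (reciprocal) |
|---|---|---|
| 5 | 0.79 | 1.27 |
| 7 | 0.85 | 1.18 |
| 9 | 0.88 | 1.14 |

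Counting the case as an event returns the ratio to 1.00 in each row. The last row extends the assumption to 9/45 = 20%.

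**Step 5: set this against the noise.** If 6 versus 6 events become 5 versus 6, the count ratio falls from 1.0 to 5/6 = 0.83, a shift of 0.18 on the log scale. The approximate standard error of the log ratio is √(1/5 + 1/6) = 0.61. The shift is about 0.3 standard errors, and the approximate 90% interval is exp(−0.18 ± 1.645 × 0.61), or 0.31 to 2.26.

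**The case against.** **The committee may already handle it.** A reader might infer that adjudicators have no way to count record B. The documents do not establish that. The operative event rule is what the committee identifies, and the algorithm figure and charter are not available; either could treat a stay ended by death as qualifying. This stands as a limit on certainty. But the SAP ties adjudication to the stated criteria, and any exception in the charter ought to appear in the SAP too.

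**The death is not lost.** A reader might also infer that record B vanishes from the efficacy evaluation. It does not. Death from any cause is a progression-free survival event (SAP 6.1.2.7), a fatal adverse event marked as respiratory deterioration counts in SAP 6.1.3.6, and adverse events leading to death are tabulated. This stands. It does not correct the hazard ratio for hospitalisation, however, because progression-free survival combines death with lung-function decline and contains no hospitalisation component.

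**Censoring at death is a recognised cause-specific analysis.** True, and it is a fair defence for record D. It is weaker for record B, where the respiratory admission did happen and only its length disqualifies it.

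**Scale.** The frequency of admissions fatal within 24 hours is unknown and probably low, and the shift from one case is small beside the sampling error. SAP 3.4 says that p-values for the other secondary endpoints will not be used for inference. All of this stands and keeps the severity low.

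**Conclusion.** The gap in the text is real: a first respiratory admission ending in death within 24 hours meets no event rule and falls under the censoring rule, with no usable censoring date. On an assumed 5 to 7 events per arm, one such case changes that arm's count by about 14% to 20% and moves an apparent hazard ratio from 1.00 to about 0.79 to 0.85 if it falls on active, or 1.18 to 1.27 if on placebo. Those figures rest wholly on assumed rates and on the case falling in one arm.

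It would be tempting to conclude that the plan favours the drug. The documents do not support that: the direction depends on which arm has the early deaths, and nothing indicates which that would be. Nor is such a subject treated as free of respiratory hospitalisation through Week 52; censoring claims freedom only up to the censoring date.

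The SAP does treat death as informative elsewhere. It gives death the worst rank in a sensitivity analysis of the primary endpoint (6.1.1.3) and counts it as progression in 6.1.2.7. SAP 6.1.2.6 has no comparable provision. This is a cheap improvement of low severity.

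**What to change.** 1. In SAP 6.1.2.6 and the adjudication charter, define the event as a non-elective respiratory admission lasting more than 24 hours or ending in death at any duration. Bring Protocol 17.2 into line at the next amendment. If the charter already contains such an exception, state it in the SAP.
2. Set the censoring date for all other deaths to the date of death.
3. Add one supplementary Cox model, with the same stratification, of time to first respiratory hospitalisation or death from any cause. It answers a different question from secondary objective 6 and should be labelled as supplementary.

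The changes should be made before blinded adjudication closes for the Core Phase database lock (Protocol 9.1.1).

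The cost is modest: a few words, one rule and one model. Admission, discharge and death dates are already on the serious adverse event form (Protocol 17.10). The downsides are that event counts will differ slightly from a strict more-than-24-hour definition, that charter and protocol wording must be aligned (Protocol 9.7 requires a formal amendment for the latter), and that any short fatal stays already adjudicated may need another look.
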